8.6 Pharmacokinetics

PK parameters will not be evaluated in this study.

8.7 Pharmacodynamics

Pharmacodynamic parameters will not be evaluated in this study.

8.8 Biomarkers

To identify novel biomarkers, the following biospecimens to support exploratory analyses of cellular components (eg, protein, RNA, DNA, metabolites) and other circulating molecules will be collected from all participants as specified in the SoA: As of Amendment 08: Biomarker samples (blood for genetic analysis, blood for ctDNA analysis, optional tumor sample), biopsies, and tumor imaging for BICR will no longer be collected. The subsection below is retained for reference.

- Blood for genetic analysis
- Blood for ctDNA analysis
- An optional tumor tissue sample for biomarker analyses may be collected, including core biopsy, bronchoscopic biopsy, or pellet from cytologic examination.

Sample collection, storage, and shipment instructions for the exploratory biomarker specimens will be in the operations/laboratory manual.

8.8.1 Planned Genetic Analysis Sample Collection

The planned genetic analysis sample should be drawn for planned analysis of the association between genetic variants in DNA and drug response. This sample will not be collected at the site if there is either a local law or regulation prohibiting collection, or if the IRB/IEC does not approve the collection of the sample for these purposes. If the sample is collected, leftover extracted DNA will be stored for FBR if the participant provides documented informed consent for FBR. If the planned genetic analysis is not approved, but FBR is approved and consent is given, this sample will be collected for the purpose of FBR.

Sample collection, storage, and shipment instructions for planned genetic analysis samples will be in the Operations/Laboratory Manual.

8.9 Future Biomedical Research Sample Collection

If the participant provides documented informed consent for FBR, the following specimens will be obtained as part of FBR:

- Leftover DNA for future research
- Leftover main study tumor tissue (including any extracted material from tissue)

• Leftover plasma or derivative for ctDNA

8.10 Medical Resource Utilization and Health Economics

Medical Resource Utilization and Health Economics are not evaluated in this study.

8.11 Visit Requirements

Visit requirements are outlined in Section 1.3. Specific procedure-related details are provided in Section 8.

8.11.1 Screening

Documented informed consent must be provided before performing any protocol-specific procedure. Results of a test performed before the participant signing consent as part of routine clinical management are acceptable in lieu of a screening test if performed within the specified time frame.

Screening procedures are to be completed within 42 days before the first dose of study intervention. except for the following:

- Laboratory tests are to be performed within 7 days prior to the first dose of study intervention.
- Evaluation of ECOG is to be performed within 7 days prior to the first dose of study intervention.
- For WOCBP, a highly sensitive pregnancy test (urine or serum) within 24 hours for urine or within 72 hours for serum prior to the first dose of study intervention. If urine pregnancy results cannot be confirmed as negative, a serum pregnancy test will be required (performed by the local study site laboratory).
- Optional tumor tissue sample collection is not required to be obtained within 42 days prior to the first dose of study intervention.

Participants may be rescreened after initially failing to meet the inclusion/exclusion criteria. Results from assessments during the initial screening period are acceptable in lieu of a repeat screening test if performed within the specified time frame and the corresponding inclusion/exclusion criteria is met. Participants who are rescreened will retain their original screening number.

8.11.2 Treatment Period Visit

Visit requirements are outlined in the SoA (Section 1.3). Specific procedure-related details are provided in Section 8.

8.11.3 Discontinued Participants Continuing to be Monitored in the Study

When a participant discontinues study intervention in the Intervention Phase, procedures for discontinuation will be performed.

The Discontinuation Visit should occur at the time study intervention is discontinued for any reason. If the Discontinuation Visit occurs 30 days from the last dose of study intervention, at the time of the mandatory Safety Follow-up Visit, the Discontinuation Visit procedures and any additional safety follow-up procedures should be performed. Visit requirements are outlined in Section 1.3. Additional details regarding participant withdrawal and discontinuation are presented in Section 7 Discontinuation of Study Intervention and Participant Withdrawal.

8.11.4 Posttreatment Visit

8.11.4.1 Safety Follow-up Visit

The mandatory Safety Follow-up Visit should be conducted approximately 30 days after the last dose of study intervention or before initiation of a new anticancer treatment, whichever comes first.

8.11.4.2 Follow-up Visits

Participants who discontinue study intervention for a reason other than disease recurrence will move into the Follow-up Phase and should be assessed every 16 weeks to monitor disease status for the first 3 years, and then every 6 months thereafter. Every effort should be made to collect information regarding disease status until disease recurrence, death, or the end of the study. Information regarding poststudy anticancer treatment will be collected if new treatment is initiated. Images will continue to be obtained after the start of the new anticancer therapy if recurrence has not been documented or verified by BICR.

8.11.4.3 Survival Follow-up

Participants who experience confirmed disease recurrence will move into the Survival Follow-up Phase and should be contacted by telephone approximately every 12 weeks to assess for survival status until death, withdrawal of consent, or the end of the study, whichever occurs first.

8.11.5 Vital Status

To ensure current and complete survival information (vital status) is available at the time of database locks, updated vital status may be requested during the study by the Sponsor. For example, updated vital status may be requested before but not limited to, an eDMC review, interim and/or final analysis. Upon Sponsor notification, all participants who do not/will not have a scheduled study visit or study contact during the Sponsor-defined period will be contacted for their vital status.

9 STATISTICAL ANALYSIS PLAN

As of Amendment 08: The Statistical Analysis Plan is amended as follows:

NOTE: Based on the data from an interim safety and efficacy analysis for KEYNOTE¬867 (data cutoff 11-JUN-2024), the eDMC recommended stopping the study since pembrolizumab in combination with SBRT did not demonstrate an improvement in event-free survival or overall survival, the study's primary endpoint and key secondary endpoint, respectively, compared to placebo plus SBRT, and the benefit/risk profile of the combination did not support continuing the trial. All prespecified interim analyses after IA1 and final analysis of the study described in the SAP will not be performed. Safety analysis will be performed at the end of the study; there will be no further pre-planned analyses for efficacy and ePRO endpoints collected from participants beyond the IA1 cutoff date of 11-JUN-2024.

This section outlines the statistical analysis strategy and procedures for the study. Changes made to primary and/or key secondary hypotheses, or the statistical methods related to those hypotheses that occurred prior to Amendment 08 were documented in previous protocol amendments, (consistent with ICH Guideline E-9). Changes to exploratory or other non-confirmatory analyses made after the protocol has been finalized, but prior to final database lock, will be documented in a supplemental SAP (sSAP) and referenced in the Clinical Study Report (CSR) for the study. Post hoc exploratory analyses will be clearly identified in the CSR. Other planned analyses (ie, those specific to the analysis of PK data and biomarker data) will be documented in separate analysis/operational plans.

9.1 Statistical Analysis Plan Summary

Key elements of the statistical analysis plan are summarized below; the comprehensive plan is provided in Sections 9.2 through 9.12.

As of Amendment 08, all the prespecified interim analyses after IA1 and final analysis of the study described in the SAP will not be performed. Safety analysis will be performed at the end of the study; there will be no further pre-planned analyses for efficacy and ePRO endpoints collected from participants beyond the IA1 cutoff date of 11-JUN-2024. The SAP summary has been updated accordingly.

Study Design Overview	This is a Phase 3, randomized, placebo-controlled clinical study to evaluate the safety and efficacy of SBRT with or without pembrolizumab in participants with unresected Stage I/II NSCLC.
Treatment Assignment	 Approximately 436 eligible participants will be randomized in a 1:1 ratio to one of the following 2 treatment arms: Arm 1: SBRT + pembrolizumab Arm 2: SBRT + placebo Randomization stratification factors are: Disease stage: Stage I, Stage II ECOG performance status: 0 or 1, 2 Geographic region of enrollment site: East Asia, non-East Asia Reason for not receiving surgery: medically inoperable vs refused surgery
Analysis Populations	Efficacy: Intent to Treat (ITT) Safety: All Participants as Treated (APaT) PRO: Full Analysis Set (FAS)
Primary Endpoints	1. Event-free survival (EFS)
Secondary Endpoints	 Overall survival (OS) Time to death or distant metastases Safety and tolerability PRO outcome
Statistical Methods for Key Efficacy/Immunogenicity/ Pharmacokinetic Analyses	The primary hypothesis will be evaluated by comparing SBRT + pembrolizumab arm to SBRT + placebo arm with respect to EFS using a stratified log-rank test. The hazard ratio (HR) will be estimated using a Cox regression model. Event rates over time will be estimated within each treatment group using the Kaplan-Meier method.
Statistical Methods for Key Safety Analyses	The analysis of safety results will follow a tiered approach. The tiers differ with respect to the analyses that will be performed. There are no events of interest that warrant elevation to Tier 1 events in this study. Tier 2 parameters will be assessed via point estimates with 95% CIs provided for between-group comparison; only point estimates by treatment group are provided for Tier 3 safety parameters. The 95% CIs for the between- treatment differences in percentages will be provided using the Miettinen and Nurminen method.
Interim Analyses	As of Amendment 08, all the prespecified interim analyses after IA1 and
	CCI

Multiplicity	CCI
	Details are provided in Section 9.9.
Sample Size and Power	As of Amendment 08, all the prespecified interim analyses after IA1 and final analysis of the study described in the SAP will not be performed. The planned sample size is approximately 436 participants.

9.2 Responsibility for Analyses/In-house Blinding

The statistical analysis of the data obtained from this study will be the responsibility of the Clinical Biostatistics department of the Sponsor.

This study will be conducted as a double-blind study under in-house blinding procedures. The official, final database will not be unblinded until medical/scientific review has been performed, protocol deviations have been identified, and data have been declared final and complete. In addition, the central radiologist(s) will perform the imaging review without knowledge of treatment group assignment.

The Sponsor will generate the randomized allocation schedule(s) for study intervention assignment. Randomization will be implemented in IRT.

Blinding issues related to the planned IAs are described in Section 9.7.

9.3 Hypothesis/Estimation

Objectives and hypotheses of the study are stated in Section 3.

9.4 Analysis Endpoints

9.4.1 Efficacy Endpoints

9.4.1.1 **Primary Endpoints**

Event-free Survival (EFS)

EFS is defined as the time from randomization to the first occurrence of the following events:

- Local, regional, or distant recurrence of disease as assessed by:
 - Radiographic recurrence by BICR

- Positive pathology by local assessment
- Physical examination by local assessment confirmed by positive pathology and/or radiographic recurrence by BICR
- Death due to any cause

9.4.1.2 Secondary Endpoint

Overall Survival (OS)

OS is defined as the time from randomization to death due to any cause.

Time to Death or Distant Metastases

Time to death or distant metastases is defined as the time from randomization to the first documented distant metastases or death from any cause, whichever occurs first.

9.4.1.3 Exploratory Endpoints

Time to Subsequent Treatment (TTST)

TTST is defined as the time from randomization to first day of next line therapy or death from any cause.

Disease-specific Survival (DSS)

DSS is defined as the time from randomization to death due to disease under study.

Time to Recurrence/Progression on Subsequent Line of Therapy (TRSLT)

TRSLT is defined as the time from randomization to the first occurrence of the following events:

- Recurrence/progression of disease by local assessment on the subsequent line of treatment
- Death due to any cause

9.4.4 Other Exploratory Endpoints

Relationships between molecular (genomic, metabolic, and/or proteomic) biomarkers and clinical response/resistance, safety, pharmacodynamic activity, and/or the mechanism of action of pembrolizumab and other treatments may be evaluation.

9.5 Analysis Populations

9.5.1 Efficacy Analysis Populations

The ITT population will serve as the population for the primary efficacy analyses. All randomized participants will be included in this population. Participants will be analyzed in the treatment arm to which they are randomized.

9.5.2 Safety Analysis Populations

The APaT population will be used for the analysis of safety data in this study. The APaT population consists of all randomized participants who received at least 1 dose of study intervention. Participants will be included in the treatment group corresponding to the study intervention they actually received for the analysis of safety data using the APaT population. This will be the treatment group to which they are randomized except for participants who take incorrect study intervention for the entire treatment period; such participants will be included in the treatment group corresponding to the study intervention actually received.

At least 1 laboratory or vital sign obtained after at least 1 dose of study intervention is required for inclusion in the analysis of the respective safety parameter. To assess change from baseline, a baseline measurement is also required.

Details on the approach to handling safety analyses are provided in Section 9.6.2.

9.5.3 PRO Analysis Population

The PRO analyses are based on the PRO FAS population, defined as participants who have at least 1 PRO assessment available and have received at least 1 dose of study intervention.

9.6 Statistical Methods

NOTE: As of Amendment 08, all the prespecified interim analyses after IA1 and final analysis of the study described in the SAP will not be performed. Safety analysis will be performed at the end of the study; there will be no further pre-planned analyses for efficacy and ePRO endpoints collected from participants beyond the IA1 cutoff date of 11-JUN-2024. The subsections below are retained for reference.

This section describes the statistical methods that address the primary and secondary objectives. Methods related to exploratory objectives will be described in the sSAP. Efficacy results that will be deemed to be statistically significant after consideration of the Type I error control strategy are described in Section 9.8. Nominal p-values will be computed for other efficacy analyses but should be interpreted with caution due to potential issues of multiplicity. If there are a small number of events in one or more strata, for the purpose of analysis, strata will be combined to ensure sufficient number of events in each stratum. Details regarding the combining of strata will be specified in the sSAP prior to database lock based on a blinded review of response counts by stratum.

9.6.1 Statistical Methods for Efficacy Analyses

9.6.1.1 Event-free Survival (EFS)

The non-parametric Kaplan-Meier method will be used to estimate the EFS curve in each treatment group. The treatment difference in EFS will be assessed by the stratified log-rank test. A stratified Cox proportional hazard model with Efron's method of tie handling will be used to assess the magnitude of the treatment difference (ie, HR) between the treatment arms. The HR and its 95% CI from the stratified Cox model with Efron's method of tie handling and with a single treatment covariate will be reported. The stratification factors used for randomization (see Section 6.3.2) will be applied to both the stratified log-rank test and the stratified Cox model.

Since disease recurrence is assessed periodically, recurrence can occur any time in the time interval between the last assessment where an event was not documented and the assessment when an event is documented. For the primary EFS analysis, the true date of recurrence will be approximated by the date of the first assessment at which an event is objectively documented, regardless of discontinuation of study medicine or missed study visits. Death is always considered as a confirmed EFS event. Participants who do not experience an EFS event will be censored at the last disease assessment (Table 7). Sensitivity analyses may be conducted using different censoring rules and will be documented in the sSAP as needed.

Situation	Primary Analysis	
Recurrence, or death documented; ≤1 missed disease assessment; and event is before new anti-cancer treatment initiation, if any	EFS event at date of documented recurrence, or death	
Recurrence or death documented; either immediately after having ≥ 2 consecutive missed disease assessments or event is after new anti-cancer treatment initiation, if any	EFS event at date of documented recurrence, or death	
No recurrence and no death; and new anti-cancer treatment is not initiated	Censored at last disease assessment	
No recurrence and no death; new anti-cancer treatment is initiated	Censored at last disease assessment	

Table 7	Censoring	Rules for	Primary	Analysis	of EFS
1.0010 /		1.00100 101		1 111001 5 010	01 D 1 N

If the proportional hazards assumption is not valid, supportive analyses using RMST method [Uno, H., et al 2014] may be conducted for EFS to account for the possible non-proportional hazards effect.

9.6.1.2 Overall Survival

The non-parametric Kaplan-Meier method will be used to estimate the survival curves. The treatment difference in survival will be assessed by the stratified log-rank test (based on the stratification factors defined in Section 6.3.2). A stratified Cox proportional hazard model with Efron's method of tie handling will be used to assess the magnitude of the treatment difference (ie, the HR). The HR and its 95% CI from the stratified Cox model with a single treatment covariate will be reported. The stratification factors used for randomization (Section 6.3.2) will be applied to both the stratified log-rank test and the stratified Cox model.

Participants without documented death at the time of analysis will be censored at the last known alive date. The Restricted Mean Survival Time (RMST) method [Uno, H., et al 2014] may be conducted for OS to account for the possible non-proportional hazards effect.

9.6.1.3 Time to Death or Distant Metastases (TDDM)

The non-parametric Kaplan-Meier method will be used to estimate the TDDM curve in each treatment group. The treatment difference in TDDM will be assessed by the stratified log-rank test. A stratified Cox proportional hazard model with Efron's method of tie handling will be used to assess the magnitude of the treatment difference (ie, HR) between the treatment arms. The HR and its 95% CI from the stratified Cox model with Efron's method of tie handling and with a single treatment covariate will be reported. The stratification factors used for randomization (see Section 6.3.2) will be applied to both the stratified log-rank test and the stratified Cox model.

Since distant metastasis is assessed periodically, it can occur any time in the time interval between the last assessment where an event was not documented and the assessment when an event is documented. The true date of distant metastasis will be approximated by the date of the first assessment at which an event is objectively documented, regardless of discontinuation of study medicine or missed study visits. Death is always considered as a confirmed TDDM event. Participants who do not experience a TDDM event will be censored at the last disease assessment.

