Treatment with pembrolizumab or placebo control will continue until 17 cycles have been administered (approximately one year), or until disease recurrence, unacceptable adverse events, intercurrent illness that prevents further administration of treatment, death from any cause, investigator decision, or participant decision or withdrawal of consent, whichever occurs first.

Participants who discontinue for reasons other than disease recurrence, or where radiographic disease recurrence has not been verified by BICR, will have posttreatment follow-up imaging until disease recurrence is documented radiographically and verified by BICR, withdrawing consent, pregnancy, death, loss to follow-up or early study termination, whichever occurs first. Images will continue to be obtained even after initiating the new anticancer therapy if recurrence has not been documented or verified by BICR.

After the end-of-treatment, each participant will be followed for the occurrence of AEs and spontaneously reported pregnancy as described in Section 8.4.

All participants will be followed by telephone for OS until death, withdrawal of consent, or the end of the study.

Specific procedures to be performed during the study, including prescribed times and associated visit windows, are outlined in Section 1.3, Table 1 of the SoA. Details of each procedure are provided in Section 8.

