8.2.1.2 Tumor Scans During the Study

The first scheduled post randomization imaging assessment (chest and abdomen CT) should be performed at 12 weeks (\pm 7 days) from the date of randomization (at least 10 weeks post completion of SBRT). This scan is considered the reference point for monitoring local recurrence (see Section 8.2.1.3), however, unscheduled imaging due to new clinical symptoms can occur at any time, including prior to the Week 12 assessment, to identify either new metastatic/regional disease or recurrence of local treated disease. Subsequent tumor imaging should be performed every 16 weeks (Q16W \pm 7 days) until 156 weeks post-randomization; and every 6 months (Q6M \pm 14 days) thereafter [Schneider, B. J., et al 2019]. Images will continue to be obtained (Q6M \pm 14 days) even after initiating the new anticancer therapy if recurrence has not been document or verified by BICR.

Timing of tumor imaging should follow calendar days and should not be adjusted for delays in cycle starts. (Note: the date imaging is performed is the date of assessment, not the date the images are reviewed.) Imaging should continue to be performed until disease recurrence as assessed by local investigator/radiologist, withdrawal of consent, pregnancy, loss to follow-up, or death, whichever occurs first. Supplemental imaging must be submitted to the central imaging vendor if it shows evidence of recurrence.

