8.2.1.4 Central Verification of Disease Recurrence

Initial tumor imaging showing site assessed disease recurrence should be submitted immediately for central imaging vendor verification of recurrence. The site and Sponsor will be notified whether the central imaging vendor verifies disease recurrence. If the central imaging vendor does not verify site-identified recurrence, the participant should remain on study (in treatment or in follow-up if treatment was completed/discontinued) until the next scheduled imaging assessment, which would again be submitted for verification of recurrence. This repeat imaging may be performed earlier than the next scheduled imaging assessment if clinically indicated. If the recurrent disease was confirmed by biopsy, repeat imaging and repeat verification of recurrence is not required.

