8.2.1.5 End-of-treatment and Follow-up Tumor Scans

If participants discontinue study intervention, tumor scans should be performed at the time of discontinuation (\pm 4-week window) unless previous scans were obtained within 4 weeks of discontinuation. If participants discontinue study intervention due to documented disease recurrence, this is the final required tumor scan.

If participants discontinue study intervention without documented disease progression, every effort is to be made to monitor disease status by acquiring tumor scans using the same schedule calculated from the date of [randomization/allocation], refer to Section 8.2.1.2.

Scans are to be continued until one of the following conditions are met:

- Disease progression as defined by RECIST 1.1 verified by BICR
- Pregnancy
- Death
- Withdrawal of consent
- The end of the study

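### TDDM: no further imaging is required after a local or regional recurrence, yet later deaths count and survivors are censored back at about that scan, so later distant metastases are incompletely captured

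*Combined protocol and SAP*

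**What the plan says.** **Endpoint.** Section 9.4.1.2 defines TDDM as "the time from randomization to the first documented distant metastases or death from any cause, whichever occurs first". Section 8.2.1.3 separates local, regional and distant recurrence, and only the last counts here.

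**Imaging.** The stopping rules refer to recurrence of any type:
- Section 8.2.1.2: "Imaging should continue to be performed until disease recurrence as assessed by local investigator/radiologist" (or until withdrawal of consent, pregnancy, loss to follow-up or death).
- Section 8.2.1.5, for those who stop treatment because of recurrence: "If participants discontinue study intervention due to documented disease recurrence, this is the final required tumor scan".
- Section 4.1: participants who stop for other reasons, or whose recurrence is unverified, "will have posttreatment follow-up imaging until disease recurrence is documented radiographically and verified by BICR".
- Section 8.2.1.4: "If the recurrent disease was confirmed by biopsy, repeat imaging and repeat verification of recurrence is not required".

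**Follow-up after recurrence.** Section 8.11.4.2 asks for disease status only up to recurrence. Section 8.11.4.3 then says: "Participants who experience confirmed disease recurrence will move into the Survival Follow-up Phase and should be contacted by telephone approximately every 12 weeks", for survival status.

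**Analysis.** Section 9.6.1.3 states "Death is always considered as a confirmed TDDM event" and, for everyone else, "Participants who do not experience a TDDM event will be censored at the last disease assessment".

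**The concern.** The event definition and the follow-up end at different points. After a local or regional recurrence the participant is still at risk for TDDM, and probably at higher risk than before, but the trial stops looking on a schedule. The analysis rule then treats participants unequally. Post-recurrence time enters the risk set for those who die and is discarded for those who do not. That is censoring determined by the later outcome, which Kaplan-Meier and Cox methods assume does not happen.

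The same wording is sound for EFS in Section 9.6.1.1, because there any recurrence is itself the event. It does not carry over to an endpoint for which local and regional recurrences are not events.

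At stake are the TDDM event count, the absolute TDDM-free rates, and a reader's understanding of a listed secondary endpoint.

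**Working it through.** The plan states no TDDM event count, effect or power, so there is no figure to reproduce. The finding comes from the text. The arithmetic only gives its likely size.

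**1. The rules applied to two participants.** Both have a verified local recurrence at the Week 44 scan (12 + 16 + 16). Both later develop distant metastases, found in routine care. One then dies and the other is alive at the cutoff.
- If the metastases were captured, both would have an event at the metastasis date.
- Under Sections 8.2.1.5, 8.11.4.3 and 9.6.1.3, the first has an event at the later death date and the second is censored at about Week 44.

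Two errors pull in opposite directions. Missed metastases raise the TDDM-free curve, and counting deaths beyond the point at which survivors are censored lowers it. A small net shift is therefore partly cancellation.

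**2. Inputs for sizing.**
- From the documents: the scan schedule (Week 12, every 16 weeks to Week 156, then every 6 months), 436 participants, and a control four-year EFS of 53% from the phase 2 trial cited in Section 2.2.4. If exponential, the hazard is −ln(0.53)/4 = 0.159 per year.
- Assumed control hazards per year: local or regional recurrence 0.05, distant 0.04, death 0.07. The sum is 0.16, and exp(−0.16 × 4) = 0.527.
- Assumed after local or regional recurrence: distant metastasis 0.25 to 0.5, death 0.12. Assumed after distant metastasis: death 0.6.
- Assumed accrual of 4 years, with the cutoff at 5.3 years.

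**3. Comparison.** Scanning until distant metastasis was compared with scanning that stops at the first detected local or regional recurrence. The death and censoring rules of Section 9.6.1.3 applied to both.

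| Quantity | Effect of stopping at recurrence |
|---|---|
| Control-arm distant metastases unseen | about 24 to 33% |
| TDDM events lost per 436 | 5 to 9 of roughly 132 to 151 |
| Three-year TDDM-free rate | overstated by about 0.6 to 2.1 points |
| Hazard ratio | moved toward 1 by about 0.003 to 0.025 |

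Taking the ends of the event ranges together, 5/132 = 3.8% and 9/151 = 6.0%. Other treatment-effect scenarios with the same control hazards widen the loss to about 3 to 6%.

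**4. Wider assumptions.** Here the local or regional share of first events was 25 to 50%, the distant share 20 to 30%, the distant hazard after recurrence 0.15 to 0.60 per year, the death hazard after local or regional recurrence 0.15, accrual 3.5 years and the cutoff 5 years.
- Unrecorded metastases range from 12 to 47%.
- 5 to 13% of all participants are censored at a local or regional recurrence scan.
- The three-year rate shifts by 0 to 3.4 points.
- In the middle scenario (40% local or regional share, hazard 0.30), the hazard ratio goes from 0.824 to 0.843 if treatment acts on all distant spread. It goes from 0.943 to 0.976 if treatment acts only on spread after a local or regional recurrence.

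**5. Scale.** With 140 events and equal arms, the standard error of the log hazard ratio is about √(4/140) = 0.169. A shift of 0.025 near HR = 1 is 0.025/0.169 ≈ 0.15 of a standard error. The most extreme case above is ln(0.976/0.943) = 0.034, or 0.20 of a standard error.

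**The case against.** Much of the opposing case stands and limits the point.

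- **A reader might infer that metastases after recurrence are unobservable.** The documents do not support that. The Survival Follow-up column in Section 1.3 also marks subsequent antineoplastic therapy and AE/SAE review. The exploratory endpoint of time to recurrence/progression on the next line of therapy (TRSLT) needs local progression assessment. Section 8.2.1 requires certain unscheduled and supplemental imaging to be sent centrally. These sources are unsystematic, though, and no section routes them into TDDM. The eCRF and supplemental SAP are not available, so a distant-site field may exist.
- **A reader might infer that TDDM is not measured as defined.** The definition concerns documented metastases, so the data can satisfy it literally. The fair criticism is that scheduled documentation stops before the risk does.
- **The stopping trigger is not simply the first recurrence.** Section 8.2.1.2 uses local assessment, while Sections 4.1, 7.1 and 8.2.1.4 rely on central verification or biopsy. Scanning continues, even after new therapy, while a recurrence is unverified. The sentence in Section 8.2.1.5 covers only those who stop treatment because of recurrence, so roughly the first year. Yet no section carries imaging through to distant metastasis once a local or regional recurrence is verified.
- **A reader might infer that the stopping decision is in doubt.** It rested on EFS and OS, which this does not touch. TDDM has no hypothesis in Section 3 and is not in Table 8.
- **The sizing rests mainly on assumptions.** The 53% figure also counts second primary lung cancer, whereas Section 8.2.1.3.2 treats a solitary lung cancer of different histology as a separate new cancer.

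**Conclusion.** The concern holds in limited form. A stated rule, not a missing detail, makes TDDM censoring depend on later survival and leaves distant metastases after a local or regional recurrence incompletely captured. Under the calibrated assumptions, roughly a quarter to a third of distant metastases go unseen and about 3 to 6% of TDDM events are lost. The three-year rate is overstated by about 0.5 to 2 points, and the hazard ratio moves modestly toward 1.

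The damage is mainly to event counts, absolute rates and interpretation, not to the between-arm comparison. All sizes depend on the assumed split of first events, the post-recurrence hazards, accrual and the cutoff. After Amendment 08 the point bears only on TDDM results from data to the IA1 cutoff.

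**What to change.** For any TDDM analysis of data to 11-JUN-2024:

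1. **Recover dates.** Use post-recurrence distant-site data already held. For participants who left imaging at a local or regional recurrence, query sites for the date of first distant metastasis up to the cutoff.
2. **Change the censoring sentence in Section 9.6.1.3.** Censor event-free participants at the last date on which distant status was known. Section 9 allows changes to non-confirmatory analyses to be recorded in the supplemental SAP before final database lock.
3. **Report and test.** Give by arm the number censored at a local or regional recurrence with no later distant assessment. Add a sensitivity analysis, labelled post hoc, that applies one follow-up limit to deaths and non-events alike, or reports distant recurrence as first event with competing risks.

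A new field at the 12-weekly telephone contact would collect nothing, because Amendment 08 ended Survival Follow-up.

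The cost is a limited site query, one changed sentence and one table, with no extra scans. The downside is that queried dates come from local, irregularly timed imaging without central review. Some may be obtained after unblinding, since Section 4.1 lets investigators apply for it before study end. Flag these dates and show results with and without them.
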